dataset for individuals who consent to take part in the research subsample. We have uploaded a variable list of the variables we will be requesting from Mirah. After the first time a youth and their caregiver complete the MBC measures, the Mirah system will proceed to screens with recruitment and consent information for participation in the Research Subsample. Youth and caregivers will be asked to assent/consent to complete additional research measures. Each time they complete Mirah measures for routine sessions, youth and caregivers will be administered one additional mechanism item; this item will be included in up to 12 sessions after they enroll in the study. In addition, they will complete a longer set of research measures will including the Ohio Scales and additional mechanism measures; these will be administered at study enrollment, 6 weeks later, and 12 weeks after study enrollment. These longer sets of research measures will be administered via the REDCap system, with links e-mailed directly to the family by research staff. Additional Research Subsample Measures have been uploaded under Study Documents. Families who consent to be a part of this Research Subsample will be paid up to \$30 for completing these measures (the project will e-mail them a \$10 gift card per major assessment completed either directly through e-mail or by using Qualtrics and Tango Card). Clinicians treating clients in the Research Subsample will also be asked to complete additional measures for those clients and will be paid \$36 for completing those measures. The Mirah system does not have a way to only recruit clients whose clinicians have consented to be in the research study or to tailor the measure schedule for those clients. Therefore, if a client agrees to be in the study and their clinician has not, the study will contact the clinician, let them know that they will be receiving links to research measures, and see whether they would like to consent to be in the study at that point. If they do not, then they will be instructed to disregard the requests for them to complete measures. These measures are also included in the Research Subsample Measures upload under Study Documents.

METHODS FOR AIM 3. MIXED-METHODS ANALYSIS OF IMPLEMENTATION FACTORS

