Aim 2b will investigate potential factors associated with condition, client, or clinician that could influence a future SMART. GLMM (MLM with a logistic linking function) will be used to investigate factors associated with treatment and attrition from the study. In addition, differences between the full RCT sample (N = 900) and the Research Subsample (N = 400) will be examined utilizing data from electronic health records (EHR) to determine whether enrollment in the Research Subsample, and completing all 12 weeks, is associated with any demographic or clinical factors. We will also examine enrollment and attrition rates for clients within clinicians to determine whether any clinician factors might be associated with client-level participation in the study, along with comparing enrollment rates across clinics. As above, these analyses will inform design of the R01 SMART, including power analyses that take into account rates of NOT/OT and projected attrition.

MLM will also be used to compare the effects of study condition on SFSS change trajectories, Ohio Scores, and MBC mechanisms (**Aim 2c**). We will examine differences in MBC outcomes by feedback condition, nesting within treating clinician and controlling for clinic. If sample sizes in the research subsample prove too small for this analytic approach, analyses of variance will be used to test a time by treatment interaction. As a first step in comparing conditions on MBC mechanisms, we will aggregate the scores across sessions (within therapist) by averaging them or summing count variables (e.g., matches between a client being identified as NOT and the therapist recognizing deterioration) to create composite variables for each mechanism domain in Figure 2.

Finally, we will extend the MLMs tested to accommodate potential mediators and moderation by NOT status, diagnosis, and treatment type (**Aim 2d**). Mediation will be tested using the products of coefficients method¹²⁹, using bootstrapping to adjust for nonnormal, asymmetric confidence intervals¹³⁰. Algorithms for testing mediation using these methods are available in the package RMediation¹³¹ available in the software platform R. Moderation by NOT status will be tested by entering NOT status, along with the feedback condition by NOT

status interaction and other model covariates. Similar models will examine moderation by diagnosis and treatment type.

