Sample size and power calculations. Given the preliminary nature of this pilot study, power calculations focused on power for the analyses of the group differences in outcomes (Hypothesis 2c.1). Power calculations were conducted using Optimal Design 3.1. We assumed 8% of the outcome variance at the clinician level¹³⁵ for an n of 22 clinicians (over the duration of the study) and 900 adolescents, $\beta = .80$, and $p = .05$. Using these estimates, Aim 2c, examining the impact of feedback condition on treatment response (assessed by the SFSS) will be optimally powered to detect a small effect of $d = .25$. The only previous estimate of differences between multidimensional and unidimensional MBC focused on the NOT subgroup only, finding an effect of ($d = .31$); the overall effect size for this study is expected to be smaller because the analyses will focus on the NOT and OT groups combined. Using a more conservative small effect size of $d = .20$ yields power of approximately .75. With respect to power assessing differences by feedback condition in the Research Subsample (n = at least 22 clinicians and 400 adolescents) will be optimally powered for a small-moderate effect of $d = .30$. Assuming an effect size of $d = .25$ yields power of .62.

DATA SECURITY, STORAGE, AND QUALITY CONTROL

Quantitative data will be collected electronically via either the University of Miami REDCAP system or directly through Mirah. Mirah is a HIPAA compliant system for collecting and scoring clinical measures. It uses Secure Sockets Layer (SSL) encryption to protect all data during transfers and stores is on a secure server. Data access will be restricted to study personnel, with permissions set to only those necessary to perform

tasks. Whenever possible, staff will download data directly from REDCAP or Mirah, but any file transfers between sites will be done via an approved secure platform such as secure send. Downloaded files will be stored on the psychology department's server, box.com, one drive, and/or google drive. The project coordinator will be regularly reviewing data for threats to data quality, such as missing data. Built-in validation protocols in REDCAP and Mirah will prevent entry of invalid responses.

Qualitative interview recordings, transcripts, and codes will also be stored securely on psychology department's server, box.com, one drive, and/or google drive.

13) Provisions to Monitor the Data to Ensure the Safety of Subjects*

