Clients and Caregivers in the Research Subsample. At least 420 clients and caregivers will complete additional research measures via the Mirah system during the Aim 1c pre-pilot and the Aim 2 trial. Consent procedures will differ slightly for the two phases of the study. For the pre-pilot, caregivers will view a consent form and youth an assent form the first time they complete these measures in the Mirah system. If they have questions before participating, they will have the option to provide a phone number and ask for a call from study staff before deciding. For the Aim 2 Research Subsample, which involves a much larger sample of youth being recruited when they start treatment, youth and caregivers will view recruitment information when they complete their clinic intake questionnaires via Mirah. If they click that they are interested in the study, they will proceed to a screen with the consent/assent document. After reading the document, they will indicate yes, no, or "I have questions." If they have questions, they will next proceed to a Frequently Asked Questions (Research Subsample Frequently Asked Questions Page, uploaded in consent materials) page to see if their question is there. If not, they will be provided with the project phone number to call to ask questions. If they indicate at the intake that they have questions and do not consent, the study recruitment and consent/assent information will be presented one more time prior to their completion of the Mirah measures for their first session. If they do not agree to be in the study at that point, they will no longer be eligible to be part of the research subsample. Because youth and caregivers receive different links to complete their Mirah questionnaires, they will be asked to assent and consent separately, and it is possible that youth may consent prior to their caregivers consenting. However, neither youth nor caregivers will complete research measures unless both have consented/assented. We are requesting a waiver of signed consent for both the pre-pilot and research subsample subsample participants. For the pre-pilot obtaining written consent would increase the study risk by providing identifying information to the study team. For the research subsample, the research

team will obtain identifying information from participants in order to give them gift cards, but the study is online, so it is not feasible to get signed consent and the study is minimal risk.

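### Aim 2c names no baseline score as a covariate, and its fallback tests a time-by-treatment interaction; adjusting for scores already collected would give a more precise comparison

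*Combined protocol and SAP*

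**What the plan says.** Section 9 makes the youth- and caregiver-reported SFSS and Ohio scales the primary endpoints, with Ohio collected in the Research Subsample only.

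For Aim 2c, section 12 (Quantitative Analyses) states that "MLM will also be used to compare the effects of study condition on SFSS change trajectories, Ohio Scores, and MBC mechanisms". The models nest clients within clinician and control for clinic. No baseline SFSS or Ohio covariate is named, and nothing says whether the arms share a mean at the first assessment. For a Research Subsample that proves too small for multilevel modelling, "analyses of variance will be used to test a time by treatment interaction". Aim 2d refers to further model covariates but does not list them.

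Baseline scores are collected. The section 8 timeline has the MBC measures given session by session. For the longer research set, which includes Ohio, section 10 says that "these will be administered at study enrollment, 6 weeks later, and 12 weeks after study enrollment".

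**The concern.** Clients are randomised 1:1, so before any feedback the arms differ on SFSS only by chance. A condition-by-time contrast with a free arm difference at baseline subtracts the whole of that chance difference. This is over-correction unless baseline and follow-up are perfectly correlated. Conditioning on baseline subtracts only the part that the correlation justifies, so under the same covariance model it is never less precise.

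What is at stake is precision on the primary endpoints, not bias: under randomisation the free-baseline contrast is valid. There is also a pre-specification gap. With the model unstated, the choice between a free baseline, a common baseline and a covariate stays open until the data have been seen.

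**Working it through.** **1. The plan's own power figures.** Section 12 (Sample size and power calculations) gives these inputs: "We assumed 8% of the outcome variance at the clinician level", and "for an n of 22 clinicians (over the duration of the study) and 900 adolescents". It states power of about .75 at d = .20 with 900 youth, and .62 at d = .25 with 400. Take a two-arm comparison with unit variance, two-sided 5% and SE = √(4/N):

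- N = 400, d = .25: SE = .100; 2.50 − 1.96 = 0.54; power .705.
- N = 900, d = .20: SE = .0667; 3.00 − 1.96 = 1.04; power .851.
- With the 8% clinician variance removed (SE × √.92): .741 and .879.
- With clients randomised within 22 clinicians, 21 degrees of freedom and a constant effect: .664 and .816.

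The stated inputs therefore give .66–.74 against .62, and .82–.88 against .75. An unstated between-clinician variance of the effect of about .02 would give .627 and .741, but the plan states no such input. The power section also mentions no repeated measures and no baseline correlation. The stated powers cannot be tied to a particular contrast.

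**2. Baseline to week 12.** Let r be the baseline-to-follow-up correlation (assumed; not in the documents).

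- Variance factor for a change score: 2(1 − r). For ANCOVA: 1 − r².
- Ratio: (1 − r²) / [2(1 − r)] = (1 + r)/2.
- r = .5, .6, .7: ratio .75, .80, .85, a cut of 25%, 20%, 15%.

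Three waves with time as a factor and compound symmetry give the same week-12 ratios.

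**3. Linear trajectories.** Scale 12 weeks to 0–1, with m equally spaced assessments, mean time t̄ and sum of squares S. Let the intercept variance be w0, slope variance w1, their covariance c and the residual variance s² = 1 − w0. For the arm differences at baseline (a) and in slope (b):

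- V(a) = w0 + s²(1/m + t̄²/S); V(b) = w1 + s²/S; C = c − s²t̄/S.
- Slope variance with no arm difference at baseline, divided by slope variance with a free one: 1 − C²/[V(a)V(b)].

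The values tried, all assumed, are w0 = .5 to .7, w1 = 0 to .4, and intercept–slope correlation 0 or −.3.

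| Case | w0, w1, correlation | V(a) | V(b) | C | Ratio |
|---|---|---|---|---|---|
| Ohio, weeks 0/6/12 (S = .5) | .5, .2, −.3 | .917 | 1.200 | −.595 | .678 |
| Ohio, weeks 0/6/12 | .7, .4, 0 | .950 | 1.000 | −.300 | .905 |
| SFSS weekly, 13 scores (S = 1.264) | .5, .2, −.3 | .637 | .596 | −.293 | .774 |
| SFSS weekly, 13 scores | .7, .4, 0 | .782 | .637 | −.119 | .972 |
| SFSS, 6 sessions (S = .7) | .6, .2, −.3 | .810 | .771 | −.390 | .757 |

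The first four rows are the extremes over the values tried for those schedules. The cut is about 9–32% for Ohio. For SFSS it is about 3–23% weekly, and about 24% in the six-session case. These are ranges over the cases tried, not bounds; fewer sessions with a smaller w0 would give a larger cut.

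**4. Order of events.**

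- Section 10: Mirah randomises clients as they are added. They then complete MBC measures, and the research invitation follows the first completion.
- Section 30: neither informant completes research measures until both have agreed, and "it is possible that youth may consent prior to their caregivers consenting". Families with questions are asked once more before their first-session measures.
- Section 10: the research measures go out by e-mailed REDCap link.

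The sequence is randomisation, arm-specific battery, consent, then Ohio. The first SFSS should precede feedback, but the Mirah measure schedule is not in the documents. Enrolment Ohio can fall after feedback has begun; no lag is given. Because subsample consent follows allocation and the arm-specific battery, equal Ohio means at enrolment are not guaranteed.

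**The case against.** The strongest reply is that the plan is silent rather than wrong. It gives no model equation. If the SFSS growth model has no condition main effect at time zero, the gain is already obtained, and the unlisted covariates in Aim 2d might include baseline. A free-baseline growth model is also legitimate, and the power section calls the study preliminary. This stands in part: the documents do not support saying that baseline adjustment is excluded. It does not reach the fallback, which is a stated method less precise than ANCOVA.

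A reader might also infer that baseline data are discarded. They are not; baseline is the first trajectory point and the first level of the time factor. Nor is the Ohio contrast shown to be a change: the reference to trajectories attaches to SFSS, and how Ohio is compared is undefined.

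A reader might want to convert the gain into a new value for the stated .62. The documents do not allow it, since that figure is not shown to refer to this contrast and does not follow from the stated inputs.

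Two tempting remedies fail. Constraining Ohio baseline means to be equal could bias the effect, because consent follows randomisation, and Aim 2b itself looks for enrolment factors linked to condition. Reclassifying an enrolment Ohio score once a feedback report has been viewed would tie baseline status to clinician viewing, a fidelity outcome compared by arm in Aim 3a.

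**Conclusion.** The point holds as a gap in efficiency and pre-specification. Aim 2c names no baseline covariate, and its stated fallback is less precise than an adjusted analysis of the same data. The cut in variance is 15–25% for a week-12 change contrast at assumed r of .7 to .5. For linear trajectories it is about 9–32% for three-wave Ohio and about 3–24% for session-by-session SFSS. Where SFSS intercept and slope are uncorrelated and sessions are frequent, the gain can be only a few per cent; the case is stronger for Ohio and the fallback.

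All of these figures rest on assumed correlations and covariances, complete data, and a planned contrast that leaves the arms free to differ at baseline. They do not show that the planned analysis is biased.

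**What to change.** State the following in section 12 before outcome data are examined:

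1. **SFSS.** Adjust for the first pre-feedback SFSS, or omit the condition main effect at that assessment. First confirm from the Mirah schedule that this score precedes any feedback.
2. **Ohio.** Define the contrast. Adjust for intake SFSS, and for enrolment Ohio where it was completed before feedback could begin. Use the covariate form, not a constrained baseline mean. Set the timing rule in advance, independently of whether a clinician viewed a report, and say how youth without a qualifying enrolment score are handled.
3. **Fallback.** Replace the time-by-treatment ANOVA with ANCOVA on the follow-up score, using the same covariates.

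Leave the stated powers unrevised on this account unless the power calculation is redone with a stated contrast and correlation. The cost is SAP wording and one check of assessment timing; no new data are needed.

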The primary study endpoints are the youth- and caregiver-reported Symptoms and Functioning Severity Scale and the youth- and caregiver-reported Ohio Problems and Functioning Scale (Research Subsample Only)

10) Procedures Involved*

Below, we present a general overview of the study methods as outlined in the grant proposal. Please note that this R34 development grant is designed to generate procedures iteratively over the course of the study, so materials and procedures will be updated and submitted as they are developed through the procedures outlined below.

METHODS FOR AIM 1: PRELIMINARY DEVELOPMENT ACTIVITIES

The goal of Aim 1 is to conduct development activities to ensure fit between agency workflow and the MBC system, implementation support tools, and research procedures. In **Development Phase 1 (Aim 1a)**, qualitative data collection will refine research measures and protocols, and assess potential implementation barriers and facilitators. Three qualitative components will be conducted with semi-structured protocols. First, either at the initial site visit or via phone or video conferencing shortly thereafter, individual or group interviews will be held with agency leaders (1-3 per clinic, for up to 15 interview participants) to help develop procedures for the pre-pilot study and discuss organizational-level factors that may influence MBC implementation. Second, individual or group interviews will also be held at the initial site visit or via phone or video conferencing shortly thereafter with up to 10 eligible clinicians combined from all five clinics. The interviews will gather information about clinical decision-making, typical clinic workflow, and any existing strategies for tracking treatment progress. Participants in individual and group interviews will respond to open-ended questions and be asked to react to sample MBC materials, study measures, and study procedures, and will be paid \$20 per hour for their time. Interviews will last 30 to 90 minutes, depending on participant availability and preferences. The interviews will be recorded and transcribed for coding, with results used to modify the project materials. The interview questions have been submitted under study documents.

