This study only presents minimal risks to participants.

14) Withdrawal of Subjects*

Participants and their parents/guardians may be withdrawn from the study without their consent if they are withdrawn from clinical care in the participating clinics. Should the client be terminated or transferred in accordance with the local clinic policy, he/she will be withdrawn from the study. In addition, participants may be withdrawn for the following reasons:

- The participant is no longer able to attend clinic visits or complete research assessments.
- There may be other reasons that are unforeseen at this time.

Those participants who voluntarily withdraw from treatment may be asked to complete the 6 and 12 week assessments for data collection purposes, if appropriate.

Clinicians may be excluded from the study for any of the following reasons:

- They leave the clinic and are no longer seeing clients at the agency.
- They are unable to attend and/or participate in training and consultation meetings.
- They are determined inappropriate for the research study (i.e. failure to adhere to treatment, failure to adhere to study procedures).

15) Risks to Subjects*

This study is considered to involve minimal risk for all participants. For the clinician and agency leader participants, participants, the main risk is that they will be asked information about their work in a group interview setting where their colleagues might hear their answers. In addition, the clinicians taking part in the pre-pilot and RCT may experience slight discomfort participating in MBC consultation calls or from seeing client progress reports. However, clinicians could experience this same discomfort in the routine supervision they receive. For youth and caregiver participants, there could be some risk of discomfort from disclosing information through the Mirah platform, although this discomfort is not anticipated to exceed that involved in typical

clinical procedures. In addition, they may experience minor discomfort giving feedback about their experiences using the MBC system.

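### The small-sample switch to analysis of variance for the Research Subsample has no trigger and no rule for missed waves; a simplified mixed model would do the same job and use incomplete informants

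*Combined protocol and SAP*

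**What the plan says.** Section 12, Quantitative Analyses (Aim 2c), compares conditions with a multilevel model, clients nested within clinician and clinic controlled. It then adds a fallback, in which "analyses of variance will be used to test a time by treatment interaction". The condition that brings the fallback into play is worded "If sample sizes in the research subsample prove too small for this analytic approach". No number, convergence criterion or decision time is attached.

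The outcomes concerned are those collected only in the subsample. Section 9 lists among the primary endpoints the "youth- and caregiver-reported Ohio Problems and Functioning Scale (Research Subsample Only". Section 10 says of the longer research measures, which hold the Ohio Scales and additional mechanism measures, that "these will be administered at study enrollment, 6 weeks later, and 12 weeks after study enrollment".

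Three places touch on missing data:
- Section 12, Data Security, Storage, and Quality Control, has the coordinator "regularly reviewing data for threats to data quality, such as missing data".
- Section 12 (Aim 2b) plans an attrition analysis, including whether enrolling in the subsample "and completing all 12 weeks, is associated with any demographic or clinical factors".
- Section 14 states: "Should the client be terminated or transferred in accordance with the local clinic policy, he/she will be withdrawn from the study". Those who leave treatment voluntarily "may be asked to complete the 6 and 12 week assessments for data collection purposes, if appropriate".

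None of these is a rule for analyzing an informant with a missed wave.

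**The concern.** A time-by-treatment analysis of variance on three waves is usually run on informants with all three. If that is what is meant, a switch triggered by scarce data would make the data scarcer: a youth or caregiver who gave enrollment and one follow-up score would be left out. Listwise deletion also needs a stricter missing-data assumption than a likelihood model, in a study that itself plans to test whether completing 12 weeks depends on client characteristics and that withdraws terminated or transferred clients. Because too small is undefined, the choice of method could also be made after the data are seen. At stake are the power and possible bias of the condition comparison on the Ohio Scales and the three-wave mechanism measures.

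**Working it through.** **The plan's own figure.** Section 12, Sample size and power calculations, gives power .62 for the subsample at d = .25, with 400 youth, 22 clinicians and 8% clinician variance. Those inputs alone give .70 to .74 with clinicians as fixed blocks, or .34 if clinicians had been randomized. A multisite formula with random effects reaches it with one added input, an unstated effect-size variance of .02. With 18 clients per clinician, the noncentrality is .25 / √[(.02 + 4/18)/22] = .25/.1049 = 2.38 on 21 df, and power is .62. The figure is therefore reachable and is not called wrong. It is not the baseline for the losses below.

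**Same test on complete data.** The split-plot interaction F was compared with the REML mixed-model F on simulated three-wave data.
- Client intercept only: 7.0966 and 7.0966 at N = 400; 0.7937 and 0.7937 at N = 40.
- Unequal arms, clinic fixed and a clinician intercept added: 3.6654 and 3.6654 at N = 60; 3.2038 and 3.2037 at N = 150.

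The client-intercept model with dropout converged in 150 of 150 datasets at each of N = 30, 40, 60 and 100 (normal data, no clinician term).

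**Cost of listwise deletion.** From the plan: three waves, 1:1 allocation, N = 400 (n = 200 per arm), alpha .05. Assumed: two-sided test, SD 1, equal correlation r between waves, enrollment always observed, enrollment-to-week-12 contrast d = .25, data missing completely at random, normal approximation, no clinician term.

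- Listwise variance: V_CC = 2 × 2(1 − r) / (n × p), with p the proportion having all three waves.
- Likelihood variance: V_L = 2 c′[Σ n_k Z_k′ S_k⁻¹ Z_k]⁻¹c, summed over the observed patterns k, with c = (−1, 0, 1), Z_k selecting the observed waves and S_k their correlation matrix.
- Power = Φ(d/√V − 1.96).

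Worked case, 80% retained at week 6 and 64% at week 12, r = .5: V_CC = 2 × 1/128 = .015625, SE .125, ratio .25/.125 = 2.00, power .516. V_L = .013958, SE .1181, ratio 2.12, power .562. Variance ratio .015625/.013958 = 1.12.

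| Pattern (week 6/week 12) | Complete of 400 | V_CC/V_L, r = .5; .7 | Power listwise vs likelihood, r = .5 | r = .7 |
|---|---|---|---|---|
| Monotone 90/80% | 320 | 1.06; 1.05 | .609 vs .635 | .823 vs .840 |
| Monotone 80/64% | 256 | 1.12; 1.09 | .516 vs .562 | .733 vs .769 |
| Monotone 60/40% | 160 | 1.22; 1.16 | .353 vs .415 | .532 vs .594 |
| Independent, 90% each | 324 | 1.15; 1.14 | .614 vs .674 | .828 vs .874 |
| Independent, 75% each | 225 | 1.45; 1.43 | .466 vs .616 | .677 vs .824 |

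Over all patterns tried, with r = .6 included, the loss is .017 to .063 (monotone) and .046 to .155 (independent). At N = 200 it is .018 to .040 and .043 to .131. For the 2-df interaction itself with a linear effect (0, .125, .25) at N = 400, it is 2 to 8 and 6 to 17 points. If the full effect is already present at week 6 the 2-df loss is larger, up to about 18 and 20 points. A separate simulation with clinician ICC .08, r = .5 and 10 to 40% missing per follow-up wave gave losses of about 6 to 24 points.

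**Bias, illustration only.** With no true effect, N = 400 and an arm-dependent missing-at-random pattern (nominal 20% and 40% missing per wave), listwise analysis of variance rejected 32% and 51% of the time; the mixed model rejected 6% and 5%.

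**The case against.** The strongest reply is that the plan never says listwise deletion. It names a class of test and leaves incomplete informants unaddressed; imputation is not ruled out. That stands: the documented defect is an unstated rule, and every loss above is conditional on the usual practice.

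Second, a reader might infer that the switch gains nothing at all. That is too strong. Equality of F holds for an uncorrected analysis of variance against a compound-symmetric model whose variance estimate is not at zero; a forced boundary case gave .267 against .327. A sphericity-corrected analysis of variance protects against something the simplest mixed model assumes. The benefit looks small: with true random slopes and 30 per arm, the uncorrected F rejected 5.2 to 5.5% under the null, the corrected test 4.7 to 5.0%.

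Third, too small may mean too few clients per clinician. Section 6 allows up to 200 clinicians; with 400 youth that is 2 each, against about 18 with 22 clinicians. The convergence check had no clinician term, so it shows only that the most reduced model fits. This argues for simplifying the random effects, not for leaving the model.

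Fourth, the reach is limited. The fallback is contingent and the study is a pilot. The follow-up offered after voluntary withdrawal and the attrition analysis would help limit or describe the loss, though neither tells the analyst what to do.

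**Conclusion.** The point holds in a conditional form. Section 12 gives no trigger for the switch, and nowhere is there an analysis rule for missed waves. If the fallback is run listwise, it drops usable informants from a primary endpoint. At N = 400 this costs about 2 to 6 power points with monotone dropout (90/80% to 60/40% retention) and about 5 to 15 with independently missed waves (90% to 75% completion), for the enrollment-to-week-12 contrast at d = .25 and r = .5 to .7. With no missed waves the cost is zero. Dropout and wave correlation are not documented, so these are ranges, not forecasts.

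Three stronger readings are not supported. All of Aim 2c does not switch: the condition refers to the subsample, so the full-sample SFSS comparison stays as planned. The plan does not commit to discarding incomplete informants. And the losses cannot be subtracted from the stated .62, because this contrast with complete data has power .71 at r = .5 and .90 at r = .7, on a different scale and without clinician variance.

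The change should be made: the loss is small to moderate and contingent, but avoidable at almost no cost.

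**What to change.** In Section 12 (Aim 2c), replace the analysis-of-variance switch with text to this effect:
- Subsample outcomes are analyzed by a REML mixed model at any sample size, using every available wave from each informant.
- If the model will not fit, it is simplified in a fixed order: drop random slopes, then the clinician intercept, keeping the client intercept and clinic as a fixed effect.
- Tests use small-sample degrees of freedom such as Kenward-Roger.
- An unstructured three-wave covariance is used where it fits; otherwise compound symmetry is checked.
- The analysis assumes data missing at random.

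This takes a few sentences and no new data. REML is already named for the Aim 1b models, and Section 22 lists SAS, Stata and HLM as available. The one downside is that the simplest model assumes compound symmetry, which a sphericity-corrected analysis of variance would not. If the investigators prefer to keep the fallback, the minimum is to define too small and state how missed waves are handled.
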